4. SELECTION AND ENROLLMENT OF PARTICIPANTS

4.1 Inclusion Criteria

Participants must meet all of the following inclusion criteria:

- 18 years of age or older prior to participating in study procedures.
- At the time of randomization, the participant's current episode/aggravation of LBP must be between 2 and 12 weeks duration.
- Participants with no LBP or less than severe LBP on average in the month prior to the current episode/aggravation are eligible.
- Average LBP severity ≥ 3 on the 0-10 numerical rating scale (NRS) over 7 days
- Medium or High Risk for persistent disabling back pain according to the STarT Back screening tool
- Ability to read and write fluently in English

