4.2 Exclusion Criteria

Candidates meeting any of the following exclusion criteria at baseline will not be enrolled:

- Average LBP characterized as severe in the month preceding the current episode/aggravation
- Specific non-mechanical causes of LBP (e.g., infection, cancer)
- Contraindications to SMT or SSM (e.g., spinal fracture, progressive neurological deficits, inflammatory arthropathies of the lower back, surgical fusion of lumbar spine)
- Active management of current episode of LBP by another healthcare provider. Participants must stop management with their current provider to enroll in the study (e.g., SMT, PT, prescription medication, CBT, a structured program led by a healthcare provider that may include pain education, mind-body practices, coping strategies etc).
 - Participants taking prescription opioid medication for LBP are required to obtain a note from a prescribing/medical provider to confirm they have safely discontinued their opioid medication.
- Serious comorbid health condition that either requires medical attention (e.g., severe hypertension, inadequately managed serious mental health conditions, substance abuse), or has a risk for general health decline over the next year (e.g., Parkinson's disease, Multiple Sclerosis, organ failure, Dementia, Alzheimer's disease).
- Pregnancy, current or planned, and nursing mothers during the study period.
- Inability or unwillingness to give written informed consent.

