6. STUDY PROCEDURES

6.1 Schedule of Evaluations

See Table on next page

Assessment	Initial Screen	Baseline/ Enrollment (Day 0)	Intervention Visits (Months 0-2)	Weekly Follow-Up (Weeks 1-52)	Follow-Up (Week 2)	Monthly Follow-Up (Months 1-12)	Follow-Up (Month 1)	Follow-Up (Month 2)	Follow-Up (Month 6)	Follow-Up (Month 12)
Informed Consent	x	x								
Demographics	x	x								
Medical History & Current Medications		x								
Physical Exam including objective outcomes		x						x		
Inclusion/Exclusion	x	x								
Technology Assessment**		x								
COVID -19 Impact		x						x	x	x
TUQ**		x					x	x		
STarT Back Screening Tool Status	x							x	x	x
Chronic LBP status (NIH RTF definition)	x	x							x	x
Chronic interference with daily activities	x	x							x	x
LBP intensity	x	x		x						
LBP frequency		x		x						
Pain Trajectory		x								x
Implementation Measures	x	x						x	x	x
Randomization/Enrollment		x								
Treatment Administered (booster sessions allowable in months 3-12)			x							

Intervention Uptake							x	x	x	x
Disability, PROMIS, healthcare and medication use, and productivity loss		x				x				
Adverse events*		x	x			x				
Satisfaction and global improvement								x	x	x
Non-specific factors (HEAL)		x			x		x	x	x	x
Psychosocial Mediators (self-efficacy, coping, kinesiophobia, and pain catastrophizing)		x						x	x	x
Participant Close Out										x

*Participants can also report adverse events to the PI's or study staff at any point during the trial
 ** Technology Assessment and the Telehealth Usability Questionnaire (TUQ) will be administered to participants who are enrolled in the 2-arm study only. Technology Assessment and the Telehealth Usability Questionnaire (TUQ) may be administered to participants in the 4-arm study if applicable (e.g., if screening and/or treatments are done virtually).

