- Low back disability will be measured with the modified Roland Morris Disability Questionnaire, a 24-item questionnaire that measures the degree to which the low back problem or leg pain restricts patients' daily activities. It has a high level of internal consistency, construct validity, and responsiveness.¹²⁰

Secondary Outcome Measures

- The PROMIS-29 Profile v2.0 Instrument (www.nihpromis.org) as recommended by the NIH RTF will be used with the exception of the question on pain intensity which is collected elsewhere on a weekly basis.⁷³ This includes the following measures: pain interference with normal activities, physical function, anxiety, depression, fatigue, sleep disturbance and the ability to participate in social roles and activities.

- LBP frequency will be collected by asking participants to report the number of days LBP has been a problem in the past 7 days.⁷³
- OTC and prescription medication use for LBP, including class and frequency by class.
- Health care utilization including provider visits, ER visits, MRIs, injections, hospitalizations, and surgeries.
- Productivity loss related to LBP (e.g., missed work, reduced productivity while at work) will be assessed using questions from the Institute for Medical Technology Assessment's productivity cost questionnaire.¹³⁷
- Physical exam objective outcome measures including QTF classification¹³³, timed up and go test, 5 times sit-to-stand test^{185, 187, 188}, and the sock test.¹⁸⁵
- Chronic interference with daily activities assessed using “how often has low-back pain interfered with your ability to do regular activities over the past 6 months?” on a 3-item scale (less than half the days in the past 6 months, at least half the days in the past 6 months, every day or nearly every day in the past 6 months).
- Prevention of cLBP at 6 and 12 months, as measured by the proportion of patients in each group meeting the definition by the NIH Task Force on Research Standards for Chronic LBP (i.e., ongoing low back problem on $\geq 50\%$ of days over past 6 months).

Psychosocial Mediator Measures

- Self-efficacy will be assessed using the 22-item Chronic Pain Self-Efficacy Scale that will be adapted for acute/sub-acute pain.¹³⁸
- Coping will be assessed using an adapted version of the 28-item Brief COPE instrument.¹³⁹

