9. STATISTICAL CONSIDERATIONS

Modifications to Statistical Analysis Plan Regarding the Sample Size and Power

(edited February 2023)

In consultation with NCCIH program staff and the DSMB in December 2022 we have modified the target enrollment to n=1000 participants (reduced from original n=1180). Our rationale for the modification is based on alignment with our updated primary outcome on chronicity. We have conducted extensive evaluation of power to detect meaningful effects using the LBP-Impact measure and our other primary outcomes. We have determined that it is appropriate to reduce the target sample size.

Modifications to Statistical Analysis Plan Regarding Primary Analysis and Treatment of Multiple Comparisons

(edited September 2022)

The trial initially had three main effectiveness objectives: (1) prevention of chronic LBP at twelve months; (2) recovery from acute/sub-acute LBP at six months; (3) Average of pain and disability over twelve months. In 2021, the NIH statistician overseeing the trial raised the question of the adequacy of the planned adjustment for multiplicity given the trial's three main effectiveness objectives and accompanying four primary outcome measures. In response to this concern, the lead investigators recommended the recovery objective be changed to a key secondary outcome. Early in the conduct of the trial it was decided and approved as a protocol change to include patients that had an acute aggravation of ongoing LBP, if the ongoing pain was not rated as severe in the month prior to the aggravation. This protocol change substantially lowers the proportion of patients that can be expected to recover according to our criteria (pain severity = 0 and RMD score ≤ 2). Given this change, the recovery outcome was less appropriate as a primary effectiveness objective and demoting it to a secondary outcome mitigates the concern of cross-objective control.

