effect using linear contrasts from a logistic regression model. Specifically, we will use two separate Wald tests based on logistic regression, with stratification by recruitment site and baseline risk group (medium, high). Let Y_{ij} denote the primary outcome status (0=not chronic; 1=chronic) for subject i in site j , and let $Site(2)$ be an indicator variable used to code the two recruitment sites. All analyses will adjust for site and the baseline risk status represented by $RiskGroup$ (0=medium risk; 1=high risk). In order to code the treatment groups we use the variables SMT (0=no; 1=spinal manipulation therapy), and SSM (0=no; 1=supported self-management). Given interruption by COVID-19 and period of restricted randomization we will adjust for this using the variables $Period(k)$ which will be an indicator for: 1=UG3 and UH3 through March 2020; 2=calendar period of restricted randomization; and 3=calendar period of resumed full factorial randomization. Regression models for the outcome are used to structure the probability of chronic back pain as follows:

$$Additive\ Model \quad \text{logit}[P(Y_{ij} = 1 | X_{ij})] = \beta_0 + \beta_1 \cdot Site(2)_j + \beta_2 \cdot RiskGroup_{ij} + \beta_3 \cdot SMT_{ij} + \beta_4 \cdot SSM_{ij} + \beta_5 \cdot Period(2)_{ij} + \beta_6 \cdot Period(3)_{ij}$$

$$Full\ Model \quad \text{logit}[P(Y_{ij} = 1)] = \beta_0 + \beta_1 \cdot Site(2)_j + \beta_2 \cdot RiskGroup_{ij} + \beta_3 \cdot SMT_{ij} + \beta_4 \cdot SSM_{ij} + \beta_5 \cdot SSM_{ij} \cdot SMT_{ij} + \beta_6 \cdot Period(2)_{ij} + \beta_7 \cdot Period(3)_{ij}$$

Our original application proposed using an additive model to generate a single summary parameter that describes the SMT effect (β_3) and the independent SSM effect (β_4). However, the additive model uses an assumption that the effect of one intervention is independent of whether the other intervention is delivered. Such an assumption is not necessary, and a full model can be used to make inference on a single linear contrast for each treatment that represents an average treatment effect.

The “Full Model” can then be used to derive an overall or average effect of SMT, and an overall or average effect of SSM. Specifically, focusing on the effect of SMT the model yields:

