likelihood ratio test of one treatment modality (either SMT or SSM). For simulations we considered crude analysis while our formal analysis will additionally adjust for site and baseline risk and therefore improve power since these are variables that only predict outcome and are not related to treatment group. For each scenario we simulated 5,000 data sets and empirically calculated power as the percentage of replicates in which the null hypothesis was rejected.

Using simulations with n=1000 subjects, 90% follow-up, and accounting for our imbalanced allocation due to COVID interruption we compute power for analyses that consider individual marginal treatment effects for both SMT and SSM. If we assume a UMC chronicity rate of 20% and a relative risk of 0.65 (rate under treatment = $20\% * 0.65 = 13\%$, or an absolute risk reduction of 7%) then we have >85% power to detect average SSM or SMT effects. If we a smaller effect corresponding to a relative risk of 0.70 (rate under treatment = $20\% * 0.70 = 13\%$, or an absolute risk reduction of 7%) then we have approximately 70% power to detect average SSM or SMT effects of this magnitude (specifically accounting for imbalance power is 72% for SSM and 70% for SMT). Power is greater for any relative risk when the UMC rate is increased to 30% or 40%. These relative risk effect sizes equate to medium effect sizes and are considered clinically important by Cochrane's Back Review Group.¹⁴⁸ We have not powered the study to detect interaction for the binary chronicity endpoint, but rather have powered the study to detect interaction on the underlying function and disability scales (see below).

Furthermore, we have excellent power to detect interaction effects where the effect of SMT and SSM may be synergistic or antagonistic, and using alpha=0.05 we have >80% to detect a X-point difference in LBP Impact treatment effects of one modality across the strata defined by the other treatment modality.

Secondary Effectiveness Outcome of Recovery: Determine the effectiveness of SMT, SSM, and the combination of SMT+SSM relative to medical care (UMC) in promoting recovery from acute or subacute LBP at 6 months.

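### The month-6 and month-12 chronicity analyses ignore NIH RTF status at entry, although it is collected and some participants may already meet the definition

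*Combined protocol and SAP*

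**What the plan says.** **Eligibility.** Section 4.1 requires a current episode or aggravation of 2–12 weeks and adds: "Participants with no LBP or less than severe LBP on average in the month prior to the current episode/aggravation are eligible". The only exclusion on earlier back pain, in Section 4.2, is "Average LBP characterized as severe in the month preceding the current episode/aggravation". Meeting the RTF definition is not an exclusion.

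**Consequence noted for recovery.** Section 9, explaining why recovery was demoted, says of admitting aggravations of ongoing pain: "This protocol change substantially lowers the proportion of patients that can be expected to recover according to our criteria". The chronicity text has no counterpart.

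**Measurement.** The Section 6.1 schedule has a row for "Chronic LBP status (NIH RTF definition"), marked at initial screen, baseline, month 6 and month 12.

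**Outcome.** Section 6.2.2 lists "Prevention of cLBP at 6 and 12 months, as measured by the proportion of patients in each group meeting the definition". Section 9 makes the 1-year status a key secondary outcome for chronicity prevention and the 6-month status another.

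**Model.** Under *Secondary Chronicity outcome Analysis*, "we will use two separate Wald tests based on logistic regression, with stratification by recruitment site and baseline risk group (medium, high"). The additive and full equations contain site, STarT Back risk group, treatment terms and period. One pair of equations is written; it is read here as serving both time points.

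**Reason for covariates.** The chronicity power text says "our formal analysis will additionally adjust for site and baseline risk and therefore improve power since these are variables that only predict outcome".

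**The concern.** The definition needs a problem lasting three months or more, with pain on half or more of the days in the preceding six months. Someone with long-standing, non-severe pain and a recent aggravation can satisfy that on day 0. If that person does not meet it at month 12, the chronic problem has resolved; onset was not prevented. If a participant who was not chronic at entry does not meet it, prevention is a fair description. The planned contrast adds the two together, and nothing planned would let a reader separate them.

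Status at entry is also likely to predict status later. The plan's own reason for covariates, that they predict outcome and so improve power, applies to it. STarT Back risk group is a different measurement and does not stand in for it.

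At stake are the interpretation of a key secondary outcome, in a trial about preventing the move from acute to chronic pain, and a few points of power for tests that the plan itself puts at about 70%.

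**Working it through.** **1. Can participants be RTF-positive at entry?** A 12-week episode is 12 × 7 = 84 days. Half of about 182 days is 91. A single new episode therefore cannot meet the definition alone. Ongoing non-severe pain before an aggravation can. So can a longer-standing recurrent problem: 84 current days plus 8 earlier days in the window is 92, even with a pain-free month before the episode. Positives at entry are thus mainly, but not only, people with an aggravation of ongoing pain.

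**2. Does another planned analysis cover it?**
- Subgroups (Sections 1.1 and 9) are STarT Back risk and duration of LBP. Section 1.1 describes duration as acute versus sub-acute.
- The case-definition check in Section 9 compares people who do and do not meet the definition on burden and characteristics. It does not split by entry status.

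**3. The plan's own power.** For n=1000, 90% follow-up, MC rate 20% and RR 0.70, the plan states "specifically accounting for imbalance power is 72% for SSM and 70% for SMT". Inputs from Section 9: rates MC 20%, SSM 14%, SMT 14%, both 8%; about 300/300/200/200 enrolled, so 270/270/180/180 evaluable; two-sided 0.05 per test. A crude likelihood ratio simulation gives 71.9% SSM and 72.4% SMT. At 310/190 enrolled it gives 73.5% and 70.5%. The stated figures reproduce.

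**4. Period adjustment comes first.** The planned model includes period, and the restricted period has no SMT arms. With no RTF-positives at all (10,000 replicates), crude power is 73.4% SMT and 72.7% SSM; with period it is 66.6% and 72.8%. The lower SMT figures below have this cause, not the missing covariate.

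**5. Adding entry status, arm rates held.** Assumptions not in the documents: share RTF-positive at entry f = 10–30%; odds ratio (OR) of 2, 4 or 8 linking entry status to month-12 status, equal in all arms; 90 MC and 90 SSM evaluable in period 2, and the other 180 per arm split 36/144 between periods 1 and 3. For an arm with overall rate P, the rate p₀ in RTF-negatives and p₁ in RTF-positives solve (1−f)p₀ + f·p₁ = P and odds(p₁) = OR × odds(p₀). The tests are Wald tests of β₃+½β₅ (SMT) and β₄+½β₅ (SSM), with 6,000 replicates.

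| OR | f | MC rate in RTF-negatives | Power SMT/SSM, as planned | Power SMT/SSM, adjusted | Share of SMT risk difference from RTF-positives |
|---|---|---|---|---|---|
| 2 | 10% | 18.7% | 65.6/73.0 | 66.3/73.4 | 15% |
| 2 | 20% | 17.5% | 66.3/73.1 | 66.8/73.6 | 28% |
| 2 | 30% | 16.5% | 67.1/71.5 | 67.5/72.3 | 41% |
| 4 | 10% | 17.2% | 66.0/72.9 | 67.3/74.7 | 20% |
| 4 | 20% | 14.8% | 67.0/72.5 | 69.2/74.6 | 37% |
| 4 | 30% | 12.8% | 65.3/72.3 | 67.4/74.8 | 52% |
| 8 | 10% | 15.6% | 67.0/72.5 | 71.5/76.8 | 24% |
| 8 | 20% | 12.0% | 67.6/73.4 | 73.7/79.0 | 46% |
| 8 | 30% | 9.3% | 67.0/72.3 | 72.1/78.2 | 63% |

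The share for OR 4, f=20%: MC splits into 14.77% and 40.93% (0.8×14.77 + 0.2×40.93 = 20.0), and the combined arm into 5.37% and 18.51%. SMT alone and SSM alone have the same rate and cancel in the average. The average SMT difference is ½(14.77−5.37) = 4.70 points in RTF-negatives and ½(40.93−18.51) = 11.21 in RTF-positives. The share is 0.2×11.21 / (0.2×11.21 + 0.8×4.70) = 2.24/6.00 = 37%.

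With a correlated risk-group term in both models (six scenarios), the gains are similar: under 1 point, about 2, and about 4–6.

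**6. Precision.** The SE of the SMT log odds ratio rises with adjustment, from 0.229 to 0.230 (OR 2) and up to 0.246 (OR 8, f=20%). The variance of the standardised risk difference falls by about 1% at OR 2, 3–5% at OR 4 and 9–13% at OR 8.

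**7. Other effect patterns.** If the plan's rates apply to RTF-negatives and RTF-positives have higher rates, with RR 0.70 in both, the gain is 0.3–3.3 points. With RR 0.85 in RTF-positives it is 0.6–11.2; the top needs f=30% and 70% of them chronic at month 12 under MC. If treatment prevents only new chronicity (separate runs without period, overall MC rate 20%, share 10–40%, relative risk 2 or 4), power is 10–53% unadjusted and 10–54% adjusted. Single scenarios gain 0.3–5.9 points, but power stays low.

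**The case against.** The strongest reply is that the target is already defined: Section 6.2.2 specifies the proportion meeting the definition among all participants, and randomisation makes that contrast valid. Adjusting for stratification factors and period is a standard choice, the outcome is secondary, and the main chronicity question has moved to LBP Impact. All of this stands, and it limits the point to efficiency and interpretation. It does not supply the missing split.

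The reply is also right that the figures rest on assumed inputs. Part of the risk-difference share is built in, because a common odds ratio gives the higher-risk stratum the larger absolute difference.

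A reader might infer more than the documents support:
- *That the treatment comparison is biased.* It is not; entry status precedes randomisation.
- *That the plan breaks its own rule*, because Section 9 adds the baseline outcome as a covariate for pain and disability. That sentence covers those outcomes only and is at most a parallel.
- *That most of any benefit would come from people already chronic.* With the pooled MC rate held at 20%, the 63% figure needs 9.3% chronicity among RTF-negatives under MC. This sits badly with a plan that calls 20% conservative and expects more in this higher-risk population.
- *That the covariate would restore SMT power.* The fall to 65–68% comes from period adjustment.

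**Conclusion.** The point holds as a modest gap in a secondary analysis. Entry criteria allow RTF-positive participants, their status is scheduled for collection, the chronicity models omit it, and no planned analysis distinguishes new from persistent chronicity under an outcome called prevention. The number of such participants is unknown from the documents.

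Under the assumed range with arm rates held, the power gain is negligible if entry status is weakly prognostic and worthwhile if it is strongly so. The split of the SMT risk difference at odds ratios of 2–4, about 15–50%, is large enough to matter for interpretation. That interpretive gain is the firmer reason to act, since it does not depend on the power gain. If treatment prevents only new chronicity, the covariate does not rescue the pooled test.

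**What to change.** In Section 9, for months 6 and 12:
- Add RTF status at entry (yes/no; day-0 record, screening record if day 0 is missing) as a covariate in the chronicity models.
- Keep the all-participant SMT and SSM contrasts as the main tests.
- Report a standardised risk difference beside the conditional odds ratio.
- Report the RTF-positive share at entry by arm.
- Pre-specify a descriptive table of new chronicity in RTF-negatives and persistence in RTF-positives.
- State that the all-participant result is chronic LBP status and combines both. Reserving the word *prevention* for RTF-negatives is optional.

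The cost is SAP wording and one table, with no new data collection. In three null settings, simulated type I error was 5.0–5.3% as planned and 5.0–5.5% adjusted. The downsides are an odds ratio that becomes conditional, with a slightly larger SE, and a split with low power. With arm rates held, RTF-negatives alone give 29–60% for SMT and 31–66% for SSM, so the table should be labelled descriptive.
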